8.2 Trial specific expected adverse events

Within DIAMOND, AEs that meet the criteria for serious will be assessed to determine if they are related and expected or not. In this trial, the events listed in the sections below are potentially expected.

8.2.1 Adverse events related to medical management (Hormonal treatments)

In this trial the following events are potentially expected with hormonal treatment:

- Change in mood
- Vasomotor symptoms
- Altered libido
- Fatigue / lack of energy
- Nausea
- Weight increase
- Headaches

For less common events please refer to the appropriate SmPC (SmPC section 4.8) to confirm if they are potentially expected.

8.2.2 Adverse events during or after laparoscopic excision or ablation of endometriosis / endometrioma and after other surgical treatment of endometriosis

In this trial the following events are potentially expected after laparoscopic excision or ablation of endometriosis/endometrioma and after other surgical treatment of endometriosis:

Intraoperative and immediate postoperative complications (Clavien Dindo grades 3-5²⁶):

- Bleeding intraoperative or postoperative >500ml
- Blood transfusion
- Injury to abdominal viscera, including bowel, bladder, ureters and blood vessels
- Laparotomy
- Colostomy
- Ileostomy
- Emergency hysterectomy
- Unplanned organ removal
- Anaesthetic complications (including hypersensitivity to the general anaesthesia and /or any of the medications or material used)
- Uterine perforation during uterine manipulation
- Admission to HDU/ITU
- Infection (wound infection, urinary tract, endometritis, pelvic sepsis, abscess, septicaemia)
- Thrombosis (Deep vein thrombosis/ Pulmonary embolism)
- Urinary retention
- Pain requiring additional analgesia
- Blood stained vaginal discharge
- Bruising/abscess/haematoma
- Return to theatre
- Any other complication not covered requiring surgical, endoscopic or radiological intervention

Late post-operative complications

- Incisional / port site hernia
- Chronic wound pain
- Infection (sepsis, septicaemia, abscess)
- Colostomy
- Ureteric stenting or reimplantation
- Fistula (e.g. vesicovaginal, ureterovaginal, rectovaginal)
- Adhesions
- Voiding dysfunction

Intraoperative, immediate or late post-operative complications can result in death, and therefore death is listed as an expected adverse event.

8.2.3 Other medications

Women may be taking other medication to reduce pain and if they report adverse events that meet the criteria for a serious adverse event, consideration will be given to the side effect profile of these other drugs.

8.3 Procedures for detecting, recording, evaluating & reporting AEs and SAEs

8.3.1 Detecting AEs

All SAEs meeting the criteria for recording within the DIAMOND trial (see section 8.1) are recorded from the time a participant consents to join the trial until the last trial follow-up. The

Investigator asks about the occurrence of relevant SAEs and complications (i.e. those that meet the criteria for recording within the DIAMOND trial) within follow-up questionnaires.

AEs that occur during or immediately after surgery for endometriosis will be captured on the surgical CRF. At 18 months, a case note review will identify any other hospitalisations for endometriosis treatment, complications of treatment etc.

8.3.2 Evaluating AEs

When a potential SAE is reported in a questionnaire, it is the responsibility of the Site Principal Investigator (or delegate) to review appropriate documentation (e.g. hospital notes, laboratory and diagnostic reports) related to the adverse event.

Assessment of Seriousness

The Investigator should assess seriousness as defined in Section 8.1.

Assessment of Relatedness (causality)

The Investigator will make an assessment of whether the SAE is likely to be related to research procedures according to the following definitions:

- **Related:** resulted from administration of any of the research procedures required by the protocol, whether or not it is either a) the specific intervention under investigation or b) it is administered outside the study as part of normal care.
- **Unrelated:** where an event is not considered to have resulted from any of the research procedures.

Alternative causes such as natural history of the underlying disease, concomitant therapy, other risk factors and the temporal relationship of the event to the treatment are considered.

Assessment of Expectedness

Expectedness will be assessed for events that meet the criteria for serious outlined in Section 8.1.

8.3.3 Recording SAEs

Notification and reporting SAEs

Site staff are responsible for notifying the trial office of any SAEs meeting the criteria for recording within the DIAMOND trial.

When an SAE form is uploaded onto the trial website, the Trial Manager is automatically notified. If, in the opinion of the local PI and/or the CI, the event is confirmed as being *serious* and *related* and *unexpected*, the CI or Trial Manager notifies the Sponsor within 24 hours of receiving the signed SAE notification; a CI cannot downgrade an assessment from the PI. The Sponsor provides an assessment of the SAE; the Sponsor cannot downgrade an assessment from the PI or CI. Any disparity is resolved by further discussion between these parties.

If, in the opinion of the local PI and/or the CI, the event is confirmed as being serious but not related or serious and expected, expedited reporting to Sponsor is not required. Rather these will be summarised and reported to Sponsor, REC, Funder, TSC and DMC in their regular progress reports.

If all the required information is not available at the time of reporting, the Investigator must ensure that any missing information is provided as soon as this becomes available. It should be indicated on the report that this information is follow-up information of a previously reported event.

8.3.5 Regulatory reporting requirements

The CI or delegate reports any SAEs that are related to any of the research procedures and unexpected to the REC within 15 days of the CI becoming aware of it using the HRA SAE form.

The CI is responsible for submitting annual reports to the REC on the anniversary of the approval.

All related SAEs are summarised and reported to the Ethics Committee, the Funder, the Trial Steering Committee and the Data Monitoring Committee in their regular reports.

8.3.6 Follow up procedures

After initially recording and reporting a SAE, the Investigator is required to follow each participant as indicated by clinical practice. Relevant follow up information on a SAE should be reported to the trial office as described above in the section above. The trial office will notify the Sponsor about any relevant follow-up information.

8.4 Pregnancy

Pregnancy is not considered an AE or SAE, however we will collect pregnancy information for trial subjects as part of the follow up questionnaires. Participants who become pregnant will be treated in line with local clinical practice.

9. Embedded qualitative work

See Appendix 1 for details

10. Sample size and proposed recruitment rate

10.1 Sample size

We need primary outcome data on 320 women at 18 months to detect an 8-point difference for the EHP-30 pain domain for 90% power (two-sided alpha 0.05) assuming a standard deviation of 22 points. The 8-point improvement was decided as a clinically important difference for the Pre-Empt trial²⁵ and has now been accepted for use by all new endometriosis trials to allow consistency and comparison of results and future metanalysis. We have assumed an attrition rate of 20% for the primary outcome, which requires us to randomise 400 women in total. The anticipated attrition rate is based on follow up data from BSGE accredited Units which have a dedicated endometriosis nurse and work to a consistent protocol which includes patient completed post-operative questionnaires at 6 and 12 months. As women with DE are all referred for treatment to dedicated endometriosis centres, they are unlikely to be lost to follow-up or choose to seek treatment elsewhere.

Attrition rates will be monitored to detect differential drop-out, which can bias clinical trial results and reduce the power of the trial to detect important differences.

10.2 Recruitment rates

Our surveys show that approximately 30 women per centre will undergo surgery for DE annually and at least 40% will be willing to be randomised. The recruitment projection is based on an estimate of 40 active centres contributing 0.8 participants per month over 22 months. This allows for staggered centre set-up and 50% reduced recruitment during the first month of site set up and 50% during the holiday months of June/July, December and April. The first 23

patients will be recruited by month 12 (recruitment month 6), 145 patients by month 18, 289 patients by month 24 and the remaining 111 by month 28, making a total of 401 participants.

The projected recruitment is modelled below in Figure 2.

10.2.1 Internal pilot study

An internal pilot stage has been included in the proposal. This 9-month pilot stage will commence in July 2021 (study month 7) and run to end April 2022 (study month 15). During this phase 28 sites will be opened and, in accordance with recruitment projections, we expect to randomise 76 subjects by the end of April 2022. The area of uncertainty we are addressing in the internal pilot is the willingness of patients to participate. Due to COVID-19, these milestones have slipped, and we anticipate recruitment commencing in month 10. Figures 2 and 3 will be updated (at the next protocol amendment) once we have established recruitment and the revised timelines are clearer.

10.2.2 Stop/go criteria

The proposed stop/go criteria are at 9 months, if we recruit:

- At least 68 participants (90% or more): We will continue without modification;
- 45–68 participants (60–90%): We will need to modify recruitment approach and continue to monitor recruitment carefully to ensure recovery manoeuvres worked.
- Less than 45 (<60%): We will enter discussions with the funder to determine whether the RCT is feasible with the possibility that the trial may need to be terminated. Full details of the stop-go criteria for the progression to the main trial will be developed in a detailed progression plan in the Statistical Analysis Plan, in consultation with the HTA Board.

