10.2.3 Project timetable and milestones

The projected timetable start date for the study was 1 January 2021: the study duration will be 52 months. Milestones: prefunding: Research Ethics Committee (REC) and HRA approvals; month 1–6, set-up, authorisations; months 7–28: patient recruitment; months 29–46: patient follow-up to 18 months post randomisation; months 47–52: data analysis, interpretation of results, report writing and dissemination. A Gantt chart is shown below (Figure 3). Due to COVID-19, these milestones have slipped, and we anticipate recruitment commencing in month 10. Figures 2 and 3 will be updated (at the next protocol amendment) once we have established recruitment and the revised timelines are clearer.

Figure 2 Recruitment Projections

[figure not shown]
[figure not shown]

Figure 3: Gantt Chart

11. Statistical analysis

All primary analyses will be based on the intention-to-treat principle. The primary outcome will be analysed using a mixed effects linear model that includes a random effect for centre and participant, with fixed effects for treatment, time, and design covariates, and baseline measure of the primary outcome. Treatment effects will be estimated at each time-point by time-by-treatment interaction. Using EHP-30 scores from each time point will increase precision of estimates. Secondary outcomes will be analysed in a similar way with generalised linear models appropriate for the distribution of the outcome (i.e. logistic regression for binary data). Sensitivities of all treatment effect estimates to missing outcome data will be explored using multiple imputation methods, and pattern mixture modelling to assess the robustness of estimates to that MAR assumption.

A secondary analysis will estimate the direct effect of receiving surgery using Casual Inference Methods. Because receiving surgery in the medical arm will be a time-dependent confounder we will use a marginal structural model (using inverse probability weights) for repeated measures data that will remove the effect of surgery in the medical arm, allowing us

to estimate the treatment effects comparing surgery to medical management without cross-over.

Full details of the statistical analyses will be documented in the Statistical Analysis Plan.

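### The pilot stop/go rule puts a count of exactly 68 in two bands and ties a nine-month decision to a ten-month window, so one boundary and the assessment date are undefined

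*Protocol*

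**What the plan says.** Section 10.2.1 of the protocol fixes the pilot window: "This 9-month pilot stage will commence in July 2021 (study month 7) and run to end April 2022 (study month 15"). It opens 28 sites in that window and gives the target: "we expect to randomise 76 subjects by the end of April 2022".

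Section 10.2.2 gives the timing, "The proposed stop/go criteria are at 9 months, if we recruit", and then three bands:

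- Green: "At least 68 participants (90% or more): We will continue without modification".
- Amber: "45–68 participants (60–90%): We will need to modify recruitment approach", with continued monitoring.
- Red: "Less than 45 (<60%): We will enter discussions with the funder" about whether the trial is feasible.

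It calls these criteria proposed and leaves their full detail to a progression plan in the SAP.

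Section 10.2.3 anchors the month count: "The projected timetable start date for the study was 1 January 2021". Sections 10.2.1 and 10.2.3 both add that COVID-19 has delayed the milestones and that recruitment is expected to begin in month 10. Neither gives a new pilot end date or a new pilot target.

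**The concern.** A progression rule has to map each possible count, read at one known time, to one action. This one fails on both parts. A count of 68 satisfies green and amber, which prescribe different actions. The assessment time is given as nine months, as study month 15 and as end April 2022, and these do not agree.

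At stake is whether the trial continues unchanged, changes its recruitment approach or goes to the funder. If the window is undefined by a month, the same recruitment performance can fall in different bands according to the date on which someone chooses to count. The record would then not show which rule governed progression. No treatment estimate, error rate or primary analysis is affected.

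**Working it through.** **Inputs (all from the protocol).** Target 76 and 28 sites (10.2.1). Cut-offs 68 and 45, labelled 90% and 60% (10.2.2). Study month 1 is January 2021 (10.2.3). Section 10.2 gives 40 centres at 0.8 women per centre per month, a 50% reduction in June/July, December and April, and milestones of 23 by month 12 and 145 by month 18.

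**1. Reproduce the cut-offs.**
- 0.90 × 76 = 68.4, printed as 68. 68/76 = 89.5%.
- 0.60 × 76 = 45.6, printed as 45. 45/76 = 59.2%.

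Both are the stated percentages rounded down, by 0.4 and 0.6 of a participant.

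**2. Check that the bands are exclusive.**
- Green is a count of 68 or more, amber is 45 to 68, red is below 45.
- Green and amber share one value, 68. Amber and red share none, since 45 is amber only.

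**3. Count the window.**
- January 2021 = month 1, so July 2021 = month 7, March 2022 = month 15 and April 2022 = month 16.
- Months 7 to 15 inclusive: 15 − 7 + 1 = 9 months.
- July 2021 to April 2022 inclusive: 16 − 7 + 1 = 10 months.
- Section 10.2 equates month 12 with recruitment month 6, so recruitment month 9 is month 15, which is March 2022.

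The nine-month and month-15 labels agree with each other. The printed end date does not agree with them.

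**4. Size of the extra month.**
- April at 28 sites, halved: 28 × 0.8 × 0.5 = 11.2 women. 11.2/76 = 14.7%.
- If a pilot is behind by a constant proportion, and 76 is the nine-month target, a count x at nine months becomes x × (1 + 11.2/76) = 1.147x at ten. Reaching 68 then needs x ≥ 68/1.147 = 59.3. Counts of about 60 to 67 at nine months (amber) would be expected to read 68 or more one month later.

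**5. Direction.** The shape of the ramp is an assumption, because the projection figure is not shown. Using cumulative recruitment that is linear to quadratic in time:
- If 76 is the nine-month target but the count is read at ten months, the projection is 76 × (10/9) = 84.4 to 76 × (10/9)² = 93.8. Then 68 is 81% to 72% of projection and 45 is 53% to 48%: lenient.
- If 76 is the ten-month target but the count is read at nine months, the projection is 76 × 0.9 = 68.4 to 76 × 0.9² = 61.6. Then 68 is 99% to 110% and 45 is 66% to 73%: strict.

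**6. Which month does 76 fit?**
- Interpolating between the stated milestones (linear, then a smooth monotone curve) gives 84 or 72 at month 15 and 104 or 97 at month 16. This favours month 15.
- Reaching 145 by month 18 from 76 needs 69 more women. The ceiling is 40 × 0.8 = 32 per month. From end April, May and June give 64, or 48 with June halved; neither suffices. From end March, April to June give 16 + 32 + 32 = 80, or 16 + 32 + 16 = 64 with June halved. So end March fits only if June is not halved.

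**7. The slipped start.** Month 10 is October 2021. Nine months from then end with month 18, June 2022, and end April 2022 would be only the seventh month. The text thus supports three assessment dates: end March, end April and end June 2022.

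**The case against.** The best defence is that this is minor drafting. The criteria are labelled as proposed, the detailed progression plan is left to the SAP, the document itself says its dates have slipped, and nine months remains as a time rule. Red leads to a discussion, not an automatic stop, and the overlap affects a single count. All of this limits the consequence. It does not remove the contradictions: thresholds and timing printed in the protocol conflict there, whatever further detail the SAP adds. Nine months also remains tied to a target dated to end April 2022.

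A reader might infer more than the document supports:

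- **That the percentages are wrong.** They are whole-number roundings, each off by less than one participant. Strictly, 68 does not meet its label of 90% or more, but that is a labelling point.
- **That the rule is lenient.** This holds only if 76 is the nine-month figure and the count is taken at ten months. The reverse pairing makes it strict, and with a month-10 start the printed date falls early.
- **That 76 can only belong to end March.** The milestones favour March, but with June halved that date falls short as well (64 against 69).
- **That the extra month is worth 22 women, or 29% of target.** That uses the full April rate (28 × 0.8 = 22.4), whereas section 10.2 halves April. Nor would a pilot at 57, which is 75% of target, become green if it stayed at that pace: 57 + 0.75 × 11.2 = 65.4, still amber.

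**Conclusion.** The point holds in a limited form. Two contradictions are certain from the text: exactly 68 falls in both green and amber, and the stated pilot dates span ten months ending in month 16, not nine ending in month 15. A third gap follows: the later start of recruitment is acknowledged but not carried through to the assessment date or the target.

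The overlap touches one count. The date error is worth about 11 women, about 15% of 76, assuming 28 active sites and the halved April rate. The direction of any bias in the decision is not established, and nothing here shows that a wrong progression decision was made. This is a wording correction that should be made; it does not affect the validity of the trial's analysis.

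**What to change.** Make the bands mutually exclusive in one of two ways:

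- Keep the printed green and red cut-offs: 68 or more, 45 to 67, below 45, with the percentages marked as rounded.
- If the percentages are to hold exactly: 69 or more (69/76 = 90.8%), 46 to 68 (60.5% to 89.5%), 45 or fewer (59.2%).

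The first removes the overlap with the least change. The second also moves a count of 45 from amber to red.

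Then state one assessment point, the end of the ninth month counted from the actual first month of recruitment, with the projected target for that month. Delete end April 2022, or correct it to end March 2022 if the original timetable is kept for reference. If the decision has already been taken, record which date, target and band were applied.

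The cost is wording only, with no change to sample size, data collection or analysis. Any SAP progression plan should carry the same bands and date.

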10.2.3 Project timetable and milestones

The projected timetable start date for the study was 1 January 2021: the study duration will be 52 months. Milestones: prefunding: Research Ethics Committee (REC) and HRA approvals; month 1–6, set-up, authorisations; months 7–28: patient recruitment; months 29–46: patient follow-up to 18 months post randomisation; months 47–52: data analysis, interpretation of results, report writing and dissemination. A Gantt chart is shown below (Figure 3). Due to COVID-19, these milestones have slipped, and we anticipate recruitment commencing in month 10. Figures 2 and 3 will be updated (at the next protocol amendment) once we have established recruitment and the revised timelines are clearer.

Figure 2 Recruitment Projections

[figure not shown]
[figure not shown]

Figure 3: Gantt Chart

11. Statistical analysis

All primary analyses will be based on the intention-to-treat principle. The primary outcome will be analysed using a mixed effects linear model that includes a random effect for centre and participant, with fixed effects for treatment, time, and design covariates, and baseline measure of the primary outcome. Treatment effects will be estimated at each time-point by time-by-treatment interaction. Using EHP-30 scores from each time point will increase precision of estimates. Secondary outcomes will be analysed in a similar way with generalised linear models appropriate for the distribution of the outcome (i.e. logistic regression for binary data). Sensitivities of all treatment effect estimates to missing outcome data will be explored using multiple imputation methods, and pattern mixture modelling to assess the robustness of estimates to that MAR assumption.

A secondary analysis will estimate the direct effect of receiving surgery using Casual Inference Methods. Because receiving surgery in the medical arm will be a time-dependent confounder we will use a marginal structural model (using inverse probability weights) for repeated measures data that will remove the effect of surgery in the medical arm, allowing us

to estimate the treatment effects comparing surgery to medical management without cross-over.

Full details of the statistical analyses will be documented in the Statistical Analysis Plan.

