	
each time point will increase precision of estimates. Secondary outcomes will be analysed in a similar way with generalised linear models appropriate for the distribution of the outcome (i.e. logistic regression for binary data). Sensitivities of all treatment effect estimates to missing outcome data will be explored using multiple imputation methods, and pattern mixture modelling to assess the robustness of estimates to that missing at random (MAR) assumption.
 
The primary aim of the trial is to compare two management strategies. However, we propose to use Casual Inference Methods to estimate the “efficacy” of receiving surgery.
 
Because receiving surgery in the medical arm will be a time-dependent confounder we will use a marginal structural model (using inverse probability weights) for repeated measures data that will remove the effect of surgery in the medical arm, allowing us to estimate the treatment effects comparing surgery to medical management without cross-over.
 
Full details of the statistical analyses will be documented in the Statistical Analysis Plan.

Co-ordination	
Local: by local research teams
 
Central: by Trial Office in Aberdeen ([contact]xxxx).
 
Overall: by the Project Management Group and overseen by the Trial Steering Committee and the Data Monitoring Committee.

Lay Summary

Endometriosis is a common condition affecting 1 in 10 women, which can cause severe pain. It happens when cells similar to those lining the womb grow outside the womb, generally on surfaces and organs within the pelvic cavity, causing bleeding, scarring and inflammation. Occasionally, rather than growing on or very near the surface, the endometriosis cells can grow deeper into tissues and organs, such as the bowel, bladder and the vagina causing a painful condition which is called deep endometriosis.

Deep endometriosis is treated in one of two ways:

- by taking hormones which can shrink areas of existing endometriosis and prevent new areas forming by stopping the growth of abnormal cells
- by using keyhole (laparoscopic) surgery to remove areas of endometriosis

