4.9 Administration arrangements post recruitment

Following trial entry, the trial office will:

- Notify the GP in writing that a participant has joined the trial.
- Write to the woman confirming her randomisation and what will happen next in the study

The site research team should:

- For those randomised to surgery, add them to the waiting list for surgery, (but can take medical treatment whilst waiting, see section 5.2)
- For those randomised to medical management, arrangements for the medical management should be made (for example commence treatment, provide a prescription or ask the GP to prescribe/administer the treatment)
- File a copy of the consent form in the hospital notes along with information about the trial.
- Enter trial data regarding the participant into the bespoke trial website.
- Maintain trial documentation at site.
- Return a copy of the signed consent form to the Trial Office in Aberdeen.

5. Trial interventions

The current clinical pathway for management of women with pain due to DE involves medical management which may end up with surgery at a later stage.

Women will be offered a choice of hormonal treatments including progestogens, combined contraceptive pill or patch, danazol and GnRH analogues (with add back hormone replacement therapy to reduce menopausal symptoms).

Women with DE randomised to the surgical arm will be offered surgery, after which women who are not trying to conceive may be offered hormonal treatment to reduce the risk of recurrence according to local centre practice/women's choice.

Women in both randomised arms (treated medically or surgically) can be offered analgesics or neuromodulators for additional pain relief. Trial participants randomised to medical management will aim to remain on their allocated medication for 18 months, alterations in medical treatment regime will be allowed but if adequate symptom relief is not achieved then surgery can be offered.

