7.4 Follow-up

Patient reported outcomes will be collected at 12 weeks, 12 months and 18 months post-randomisation using questionnaires completed by women at home. The questionnaires will include EHP-30 + Section C, EQ-5D-5L, symptoms, and questions about current and recent treatment (including analgesic use), satisfaction with treatment, serious adverse events/complications, and any pregnancy.

While the chances of pregnancy are very low (based on our eligibility criteria), we will collect and analyse data on women who become pregnant during the follow up period.

At baseline, participants will be asked for their contact preferences for questionnaires. Those selecting email as their preference will have a link to the questionnaire emailed to them. Those selecting post as their preference will have the questionnaire posted to them. Those selecting text messaging as their preference will have a link to the questionnaire texted to them. First reminders will be emailed, posted or texted to participants (according to their stated preference). A second reminder (by telephone) will be attempted but if there is no response by telephone, a final postal reminder will be sent.

Questionnaires will be administered to all women who were randomised in the study, regardless of their compliance to the randomised treatment unless they have opted out of questionnaire follow-up. This means that patients who have not received their allocated treatment, have received the non-randomised treatment or have discontinued medical management will continue to be followed up in the study.

If questionnaires are returned as non-deliverable, attempts will be made by site staff or staff at the Trial Office to trace the participant.

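### The secondary causal analysis names two different targets, adjusts for surgery in the medical arm only, and calls that surgery the confounder when it is the treatment

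*Protocol*

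**What the plan says.** The primary analysis is by intention to treat and compares two management strategies. Section 11 then adds a further aim: "A secondary analysis will estimate the direct effect of receiving surgery using Casual Inference Methods". The Trial Summary (Statistical methods) puts it as "Casual Inference Methods to estimate the “efficacy” of receiving surgery".

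Both places give the same method: "receiving surgery in the medical arm will be a time-dependent confounder we will use a marginal structural model (using inverse probability weights". The model is meant to "remove the effect of surgery in the medical arm", allowing the team "to estimate the treatment effects comparing surgery to medical management without cross-over".

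Two other passages bear on this. Section 5 says of women in the medical arm that "if adequate symptom relief is not achieved then surgery can be offered". Section 7.4 says that "patients who have not received their allocated treatment, have received the non-randomised treatment or have discontinued medical management will continue to be followed up".

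The protocol names no covariates for the weights and leaves full detail to the SAP. It gives no expected rate of surgery in the medical arm or of non-receipt in the surgical arm.

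**The concern.** An effect of receiving surgery compares women who are operated on with women who are not. The stated adjustment deals with departures in one arm only. Women allocated to surgery who decline it, or who are still waiting, get no adjustment, so they pull the surgical-arm mean towards that of unoperated women. The result could then be published as the efficacy of surgery when it is the effect of being allocated to surgery, with medical-arm cross-over removed.

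The label matters as well. Inverse probability weights come from a model of treatment given confounders. A text that names the treatment as the confounder, and names no actual confounder, gives whoever writes the SAP the wrong starting point.

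**Working it through.** **1. The plan's own figures.** Section 10.1 uses a difference of 8, SD 22, two-sided alpha 0.05 and 90% power. Per arm, n = 2 × (1.960 + 1.282)² × 22² / 8² = 2 × 10.51 × 7.5625 ≈ 159, or 318 in total against 320 stated. Allowing for 20% attrition, 320 / 0.80 = 400. Both figures reproduce. The causal analysis has no figure of its own, so the 8 points serve below only as a scale.

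**2. The two targets side by side.**

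| Wording | Contrast implied | Departures to be handled |
|---|---|---|
| Effect, or efficacy, of receiving surgery | Operated versus not operated | Surgery in the medical arm and non-receipt in the surgical arm |
| Surgery versus medical management without cross-over | Allocated to surgery versus medical management with no surgery | Surgery in the medical arm |

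The stated method fits the second row. It fits the first only if receipt in the surgical arm is complete and timely.

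**3. Does the protocol assume complete, timely receipt?** It does not.
- Section 2.2 counts movement from the medical arm to surgery and the reverse.
- Section 5.2 puts surgical-arm women on a waiting list with no time limit, and has the research nurse confirm that the operation took place.
- Footnote 2 of Table 2 (Section 7.1) separates those randomised to surgery who have it.
- Sections 7.4 and 7.6 keep women who do not get their allocated treatment in follow-up.
- Appendix 3 allows for waiting-list delays.

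**4. Size of the mismatch.** Let d be the true effect of receiving surgery and q the share of the surgical arm not operated on. Assume that unoperated women gain nothing and that the medical-arm correction is perfect. The estimate is then d × (1 − q). With d = 8:
- q = 0%: 8 × 1.00 = 8.0
- q = 5%: 8 × 0.95 = 7.6
- q = 10%: 8 × 0.90 = 7.2
- q = 20%: 8 × 0.80 = 6.4

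The values of q are assumptions. Late surgery is a further departure, which the protocol's figures do not allow anyone to size.

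**5. Roles of the variables.** A time-dependent confounder changes over time, influences later treatment and predicts the outcome. Under Section 5, inadequate symptom relief leads to surgery, and current symptoms predict later pain. Symptoms therefore fit the definition. Surgery in the medical arm is the event whose probability the weights model, so it is the time-varying treatment.

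**6. Age of the scheduled pain data.** Table 2 and Section 7.4 place questionnaires at baseline, 12 weeks, 12 months and 18 months. The widest gap is 52.2 − 12 = 40.2 weeks, or 9.2 months; the next is 6 months. Scheduled pain scores can therefore be about 9 months old when a woman crosses over.

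**The case against.** The strongest reply is that Section 11 states the contrast it will deliver, surgery against medical management without cross-over, and that weighting in the medical arm can estimate that contrast if the confounders are measured. This stands. A reader might infer that the analysis cannot estimate anything it claims, but the documents do not support that. The method misses only the first of the two stated targets.

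It can also be said that a marginal structural model with inverse probability weights is the standard tool here and that the weight model is ordinary SAP content. This stands too. A reader might infer that the weights will be built from the wrong variable, or from 12-week pain alone. Neither is in the text. Reasons for discontinuation, further treatments, case notes and prescription records are also collected and could inform the weights. Any figure for bias from old pain scores would rest wholly on an assumed weight model and assumed cross-over rates, so none is claimed here. What remains of the 9-month gap is a limitation of the data that the SAP cannot remove.

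Non-receipt may also be small. Women with a treatment preference are excluded (Section 4.3), and Appendix 3 reports advanced endometriosis lists running at normal levels. That bears on the size of the dilution. It does not remove the mismatch, because the protocol still provides for unoperated women and gives them no place in this analysis. The protocol does not say how they will be coded, so one cannot assert that they will be treated as operated on. An SAP that models actual receipt in both arms would resolve the point.

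**Conclusion.** The point holds as a mismatch between aim and method. One secondary analysis carries two targets, and the one-sided adjustment serves only allocation to surgery versus medical management without cross-over. Read as the effect of receiving surgery, the estimate shrinks in proportion to non-receipt: 8 points become 7.2 at 10% and 6.4 at 20%. This assumes no gain without surgery, a perfect medical-arm correction and rates that the protocol does not give. The confounder label is wrong in both places where it appears. The finding does not touch the primary intention-to-treat analysis or the sample size.

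**What to change.** In Section 11 and the Trial Summary, and correspondingly in the SAP:

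- State one estimand for this analysis.
- Name dated receipt of surgery as the time-varying exposure, and symptoms and treatment changes as the time-dependent confounders.
- If the target is receiving surgery, apply the weighting to departures in both arms (surgery in the medical arm, non-receipt in the surgical arm) and say how late surgery is counted in the analysis.
- Otherwise drop the receiving-surgery and efficacy labels, and report the result as allocation to surgery versus medical management without cross-over.
- Report as a limitation that scheduled pain scores may be about 9 months old at cross-over. Weights for non-receipt in the surgical arm would share it.
- Optionally, add a complier-average (CACE) estimate with allocation as instrument, as a sensitivity analysis. It is a different estimand. Its monotonicity and exclusion assumptions must be stated, and the exclusion restriction is open to doubt because hormones are allowed in both arms and the timing of surgery varies.

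The surgical CRF covers operations in either arm (Section 7.3), and the 18-month case-note review (Section 7.5) adds further treatment, so no new data are needed. The cost is redrafting and wider confidence intervals in a secondary analysis.
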